An SBRT treatment plan will be developed based on tumor geometry and location. Institutional standards for radiation quality assurance and radiation delivery will be utilized. The tumor volume (GTV), as identified on the treatment planning CT, will be contoured by an attending physician from UC Radiation Oncology. The final GTV will be defined by the attending radiation oncologist after reviewing the diagnostic CT, respiratory-correlated 4D-CT scan, pancreas protocol CT scan. These scans will be used to define the ITV (internal target volume). The final PTV (planning treatment volume) expansion will consist of an additional 2-3mm of margin expansion of the primary tumor to generate the PTV primary, except if the margin results in expansion into the duodenum or stomach. In these cases, margin expansion is allowed to be non-uniform. The dose will be prescribed to the isodose line that completely surrounds the PTV primary. It is recommended that 6-12 co-planar fields be used in the radiation treatment plan. A low dose clinical target volume will also be incorporated in the treatment volume called CTV vasculature. This customized CTV volume covers the immediately abutting vasculature (SMA, celiac, SMV), the pathway of perineural spread to the root of the mesentery, and extrapancreatic tissue immediately adjacent to the primary tumor at the discretion of the radiation oncologist. A 3 mm PTV margin will be added to the CTV vasculature to generate the PTV vasculature. The dose to this structure will receive 25 Gy over the 5 fraction SBRT course.

Contours of the fiducials used for target localization will be generated on the applicable image sets, to be used for patient setup on treatment. Radiation dose to the adjacent normal tissue will be minimized. Based on an analysis of duodenal toxicity representing pooled data from 3 previous prospective studies, the following dose constraints must be met: V15<9cc, V20<3cc. The duodenum (duo@PTV) as defined for these dosing parameters includes the entire duodenum on the same axial plane as the PTV and duodenum 1 cm above and 1 cm below the PTV. V15 and V20 are defined as the percent volume receiving 15 Gy and 20 Gy, respectively. The remainder of the normal tissues will be limited as follows:

- Liver (excluding tumor): 50% should be limited to <12 Gy
- Kidney: Combined volume for both should have 75% <12 Gy

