- Stomach and duodenum: V15<9cc and V20<3cc. 50% should be limited to <12 Gy (no more than 1 cc of proximal stomach can receive >33 Gy)
- Spinal Cord: no more than 1cc can receive >8 Gy

No more than 1cc of the PTV primary can receive >130% of the prescription dose (4290cGy for 6.6Gy x 5).

Greater than 90% of the PTV primary should receive 100% of the prescription dose (3300cGy for 6.6Gy x 5)

Greater than 90% of the PTV Vasculature should receive 100% of the prescription dose (2500 for 5 Gy x 5)

If above constraints cannot be achieved, then 100% of the GTV must receive at least 25 Gy (an allowed minor deviation, which will be documented). If this constraint cannot be met, the patient should be removed from the protocol.

Linac based SBRT Treatment Delivery

Patients will receive 5 fractions of 6.6 Gy delivered twice weekly, with each fraction separated by

> 48 hours. Radiotherapy will be delivered Monday- Friday at Precision Radiotherapy or Barrett Cancer Center. Initial patient positioning will be based on volumetric kV (cone-beam CT) imaging with shifts to bony anatomy as appropriate. Orthogonal kV/MV or kV/kV projection imaging will be used to verify the location of the fiducials prior to delivery of first treatment beam. A secondary shift based on the location of fiducials may be utilized, as indicated by the position of the fiducials. For free-breathing treatments, kV fluoroscopic images should be obtained to confirm the anticipated position of these fiducials during the entire respiratory cycle. Active monitoring of treatment delivery accuracy will be accomplished using kV and/or MV projection imaging, either immediately before or during all (or a subset of) treatment fields. Patient-specific dosimetric quality assurance (QA) will be performed as per standard practice in the Department of Radiation Oncology at University of Cincinnati.

Post-Linac based SBRT Follow-Up

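### The planning fallback does not say which constraints may yield, so read literally it overrides the mandatory duodenal dose limits, whose unit is also misdefined

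*Combined protocol and SAP*

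**What the plan says.** All the text at issue is in Section IV, Treatment Planning.

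- The duodenum has a mandatory rule: "the following dose constraints must be met: V15<9cc, V20<3cc". It applies to the duodenum at the level of the PTV and 1 cm above and below (duo@PTV).
- The unit is then set: "V15 and V20 are defined as the percent volume receiving 15 Gy and 20 Gy, respectively".
- A list of further limits follows. It repeats the same two cc limits for stomach and duodenum together. Some entries are worded as goals, such as "Liver (excluding tumor): 50% should be limited to <12 Gy". Others are flat limits, such as "Spinal Cord: no more than 1cc can receive >8 Gy" and the hot-spot rule, "No more than 1cc of the PTV primary can receive >130% of the prescription dose". Coverage is a goal: "Greater than 90% of the PTV primary should receive 100% of the prescription dose", with a parallel goal for the PTV vasculature at 25 Gy.
- The list ends with the fallback: "If above constraints cannot be achieved, then 100% of the GTV must receive at least 25 Gy (an allowed minor deviation", to be documented). The next sentence removes a patient from the protocol only if this 25 Gy condition fails.

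**The concern.** The fallback refers back to the constraints above it without distinguishing mandatory limits from goals. Taken at its word, it covers the duodenal limits, the cord, proximal-stomach and hot-spot limits, and the coverage goals alike. One plan can then be barred by one sentence and allowed by another in the same subsection.

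The duodenum is where this matters most. Section VIII names duodenal and gastric ulcers as the major toxicity, and its expectation of a low ulcer risk (under 5%) rests partly on a lower duodenal dose than in prior studies. Section IV derives the two limits from pooled toxicity data. The primary endpoint in Section IX is acute grade 3 or higher GI toxicity. The fallback governs the hardest anatomy, where target dose and bowel limits compete. Two planners could accept and reject the same plan, and a breach would be filed as minor.

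The unit definition adds a second uncertainty about the same limits: whether the number to check is a volume or a percentage.

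**Working it through.** **1. The rules side by side.** Each row is a type of plan.

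| Plan | Mandatory duodenal sentence | Fallback, literal | Fallback, coverage only |
|---|---|---|---|
| Limits met, coverage met | accept | not needed | not needed |
| Limits met, coverage missed, whole GTV at 25 Gy or more | satisfied | accept, minor deviation | accept, minor deviation |
| Duodenal limit broken, whole GTV at 25 Gy or more | refuse | accept, minor deviation | refuse or replan |
| Whole GTV reaches 25 Gy only by breaking a duodenal limit | refuse | accept, minor deviation | remove |
| Whole GTV cannot reach 25 Gy at all | no bearing | remove | remove |

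The readings part in the third and fourth rows. No other section says which column applies, and nothing caps how far a limit may be exceeded under the literal one.

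**2. The unit.** A limit of L cc in a structure of V cc is 100 × L / V percent. The documents give no volume for duo@PTV, so V is an assumption here, taken from 30 to 100 cc.

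| Assumed V | 3 cc as percent | 9 cc as percent |
|---|---|---|
| 30 cc | 10.0% | 30.0% |
| 50 cc | 6.0% | 18.0% |
| 100 cc | 3.0% | 9.0% |

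Reading the limits as 3% and 9% gives the same rule only at V = 100 cc. Below that volume the percent reading is stricter: at 50 cc, 3% is 1.5 cc and 9% is 4.5 cc.

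**3. The doses involved.** The protocol's linear-quadratic formula is BED = D × (1 + d / (α/β)), with total dose D and dose per fraction d over 5 fractions. It first reproduces the two five-fraction rows of Table 1:

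- 33 Gy (d = 6.6): early (α/β = 10) 33 × 1.66 = 54.8; late (α/β = 3) 33 × 3.2 = 105.6.
- 25 Gy (d = 5): early 25 × 1.5 = 37.5; late 25 × 2.667 = 66.7.

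The late values at the duodenal dose levels are:

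- 15 Gy (d = 3): 15 × 2 = 30.0.
- 20 Gy (d = 4): 20 × 2.333 = 46.7.

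So V15 restricts to under 9 cc the duodenum at late BED 30.0 or more, and V20 restricts to under 3 cc the volume at 46.7 or more. Under the literal fallback neither restriction binds. These figures locate the limits on the dose scale; they do not measure harm.

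The fallback floor is 25 / 33 = 76% of the prescribed dose, and its early BED is 37.5 / 54.78 = 68% of the prescription's. It is a minimum to the GTV, whereas 33 Gy is the prescription to the PTV primary.

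**The case against.** The strongest reply is that the intent is plain. What the fallback prescribes is a lower target dose, and giving up about a quarter of it makes sense mainly as a way to keep the organ limits. The surrounding text points the same way: the duodenal limits are mandatory, normal-tissue dose is to be minimised, and the PTV margin may be shaped to stay out of duodenum and stomach. On this view the minor deviation is the reduced coverage and nothing else. Likewise, percent is probably a slip, since every stated V15 and V20 limit is in cc.

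Most of that stands as an account of intent. It does not supply the missing rule. The fallback is used exactly when a planner must choose what gives way, and treatment is delivered at either of two locations. If the intent is agreed, writing it down takes a sentence.

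Three stronger inferences are tempting and not supported:

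- *That the plan means to allow duodenal overdose, or that toxicity would rise.* The documents give no frequency for the fallback and no dose-response figure, so neither can be shown.
- *That the prescription rule, "The dose will be prescribed to the isodose line that completely surrounds the PTV primary", contradicts the coverage goal of more than 90%.* The first can be read as a prescription convention and the second as an acceptance tolerance, and the two can coexist. Aligning them would be a clinical change, not a correction.
- *That a removal at planning leaves the final toxicity rule undefined at 19 patients.* Section IX (Toxicity Stopping Rules) defines the toxicity rate over treated patients, so someone removed before any fraction is outside the denominator and the proportion threshold can still be applied. Section IX states no replacement rule, but that is a separate matter and no change to it is proposed here.

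**Conclusion.** The point holds as a conflict in the written plan-acceptance rules. The mandatory duodenal limits and an unrestricted fallback cannot both govern a plan that breaks a limit but gives the whole GTV 25 Gy. The definition of V15 and V20 also does not match the unit of the limits. The first defect bears on safety; the second is probably editorial, but it affects the same two numbers.

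The size can be stated only in terms of the rules: under the literal reading, two mandatory volume limits cease to bind. How many plans this would reach cannot be determined from the documents. No change in toxicity rate, sample size or error rates is claimed. The conclusion assumes only that the current Section IV text is what planners follow. The change should be made, but the trial's validity does not hang on it.

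**What to change.** Two wording changes in Section IV, Treatment Planning:

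1. Define V15 and V20 as the absolute volume, in cc, receiving at least 15 Gy and at least 20 Gy.
2. Replace the fallback and the removal sentence with: *If the PTV primary or PTV vasculature coverage goals cannot be achieved while the organ limits are met, coverage may be reduced, provided the whole GTV receives 25 Gy or more (minor deviation, documented). The duodenal and stomach V15/V20, proximal stomach, spinal cord and 130% hot-spot limits still apply. If the GTV cannot receive 25 Gy within these limits, the patient is removed from the protocol.*

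The investigators should confirm the stomach V15 and V20 limits, which carry neither mandatory nor advisory wording at present. The liver, kidney and half-volume stomach and duodenum entries are worded as goals, and the new text does not turn them into grounds for removal.

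The cost is an amendment of a few sentences, with no new procedure. Holding the limits may remove a few more patients at planning than the literal reading would; the number cannot be determined from the documents.

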SECONDARY OBJECTIVES	To evaluate rates of late (> 3 months after treatment) gastrointestinal toxicity following fractionated Linac based SBRT for pancreatic tumors. Toxicities of note include grade 2 or greater gastritis, enteritis, fistula, or ulcer and any other grade 3 or greater gastrointestinal toxicity. To evaluate local progression free survival, overall survival and metastasis-free survival rates after Linac based SBRT and subsequent resection in patients with resectable and/or borderline resectable pancreatic adenocarcinoma of the head and/or body. To develop and standardize Linac based SBRT delivery and dosimetric parameters. To estimate resection margin positivity (R0/R1) and pathologic complete response rate after neoadjuvant SBRT To evaluate pre- and post- SBRT patient reported quality of life (QOL)
TREATMENT	After 3- 4 months of chemotherapy, patients will be enrolled to a single arm trial of stereotactic body radiotherapy (SBRT) in 5 fractions given over 15 days. They will then proceed to surgery after a break of 4-6 weeks.

INCLUSION CRITERIA	
 • Age >18 years. • Karnofsky Performance Status >70% (see Appendix IV). • Histologically confirmed pancreatic adenocarcinoma of the head and/or body; at least the majority of the histopathologic specimen must be identified as adenocarcinoma. • Pancreatic tumors must be considered at least borderline resectable and/or borderline resectable at time of treatment planning. Definition of resectable and/or borderline resectable: no metastases, less than 180 degree involvement of hepatic artery, superior mesenteric artery or celiac artery • No active infection requiring hospitalization • If bilirubin > 2, patients must have a biliary stent placed prior to SBRT. • Patients must have acceptable organ and marrow function (see section “Inclusion Criteria, page 17-18). • Women who are not post-menopausal (as defined in Appendix V) should have a negative urine or serum pregnancy test. Women of childbearing potential must agree to use adequate contraception for the duration of study participation. • Ability to understand and the willingness to sign a written informed consent document. • Life expectancy > 3 months. • Patients are to have received neoadjuvant chemotherapy prior to enrollment. Approved regimens may consist of 3-4 months of gemcitabine-based chemotherapy or FOLFIRINOX. Patients will have a 2-4 week break between last chemotherapy administration and start of

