- Pathologic confirmation of malignancy. (Core biopsies during gold fiducial placement as needed or optional). Patients are encouraged but not required to have tissue banked in UCCI Tumor Bank per Tumor Bank protocol.
- Pancreas protocol CT required; if patient allergic to contrast and allergy can not be premedicated with steroids prior to IV contrast, pancreas protocol MRI will be obtained
- Baseline collection of EORTC QLQ C-30/ PAN26 QOL.

Fiducials

Treatment on this protocol requires placement of 1-5 gold (99.9% pure, 1-5 mm length, or visicoils) fiducials for targeting purposes. The fiducials will be used as surrogates for targeting the daily tumor position during treatment. The fiducials will be placed directly into the tumor and/or periphery under endoscopic ultrasound or CT guidance. When possible, clips or fiducials will also be placed in the proximal duodenum directly adjacent to the pancreatic tumor. Fiducials may be implanted prior to enrollment as this is an acceptable standard of care procedure for any patient receiving radiotherapy for pancreatic cancer.

If fiducials are not placed intraoperatively and/or prior to enrollment, placement will be done and is expected to be done on an outpatient basis. In rare occurrences when fiducials/clips cannot be placed, patients may be treated at the discretion of the PI.

Simulation

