Stereotactic radiotherapy will be performed using Linac based radiation machines. The radiation treatment plan will be designed to use multiple beams of radiation to concentrate large doses of radiation within a tumor. The Linac machines are equipped with cone beam CT imaging that can

be used to deliver image-guided radiation therapy (IGRT). IGRT allows delivery of highly accurate, stereotactic radiation treatment. The use of cone beam CT images during IGRT is considered standard of care treatment. Uncertainties in tumor location are minimized because these machines have on- board, volumetric imaging for accuracy in initial patient setup; KV and MV projection imaging during treatment is used to monitor delivery accuracy and/or make corrections to the patients' position.

V. STUDY POPULATION

PATIENT SELECTION

Inclusion Criteria

- Age >18 years.
- Karnofsky Performance Status >70% (see Appendix IV).
- Histologically confirmed adenocarcinoma of the pancreatic head and/or body; at least the majority of the histopathologic specimen must be identified as adenocarcinoma as opposed to another histologic subtype.
 - *If histological confirmation of adenocarcinoma cannot be obtained by biopsy, the following procedures may be employed:
 - Attempt a repeat biopsy to obtain a diagnosis.
 - Present the case at UC tumor board and if the candidate has one of the following: a rising CA 19-9 or radiographic evidence of pancreas tumor on MRI, CT, and/or PET scan then the patient can be considered for treatment on protocol.
 - However, if these objectives cannot be met, the patient will not be a candidate.
- Pancreatic tumor must be considered at least borderline resectable by UC multi-disciplinary tumor board at the time of treatment planning.
- Patients who have not received RT to the abdomen.
- Patients must have acceptable organ and marrow function as defined below (within 2 weeks prior to radiotherapy):
 - Leukocytes >3,000/ μ L
 - Absolute neutrophil count >1,500 μ L
 - Platelets >100,000/ μ L
 - Total Bilirubin \leq 2X normal institutional limits
 - AST(SGOT)/ALT(SGPT) <2.5X institutional upper limit of normal
 - Pre-menopausal women must have a negative serum pregnancy test
 - If bilirubin > 2, all patients must have a biliary stent placed prior to radiotherapy. After stent placement, bilirubin must be <1.5x normal prior to study entry.
 - Creatinine \leq institutional upper limit of normal
- OR

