All late AE and the maximum grade for each type of adverse events (including all adverse events and those that are possibly, probably or definitely related to study treatments) will be recorded for each patient. The frequency tables will be reviewed to determine the patterns. Point estimate and confidence interval will be reported for binary endpoints. All patients meeting the eligibility criteria and confirmed by central review who have signed a consent form and have begun any dose of treatment will be evaluable for the following secondary endpoints, unless otherwise specified.

- The positive margin resection rate is defined as number of patients achieved R0 versus R1/R2 resection during surgery divided by number of evaluable patients. (R0= negative margin, R1= microscopically positive margin, R2= macroscopically positive margin). Point estimate and confidence interval of the rate will be reported.
- The histopathologic response rate is defined as number of patients achieved CR or PR determined according to histopathologic examination during pre-operative chemo or chemoradiotherapy divided by number of evaluable patients. Point estimate and confidence interval of the rate will be reported.
- Time to locoregional recurrence is defined as time from the date of registration to the date of the first documented locoregional recurrence. The Kaplan-Meier methods will be used to estimate the median time, and event-free rate at specific time points (6 month, 12 month, etc.).
- Time to distant recurrence is defined as time from the date of registration to the date of the first documented distant recurrence. The Kaplan-Meier methods will be used to estimate the median time, and event-free rate at specific time points (6 month, 12 month, etc.).
- Overall survival is defined as time from the date of registration to the date of the death due to all causes. The Kaplan-Meier methods will be used to estimate the median time, and event-free rate at specific time points (6 month, 12 month, etc.).

Safety Stopping Rules

In addition to toxicity feasibility stopping rules, accrual will be temporarily suspended to the study, if at any time, we observe events considered at least possibly related to study treatment an adverse event with attribute specified as ("possible," "probably," or "definite") that meet the following:

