APPENDIX I

STUDY CALENDAR

	Pre-Study	Pre-SBRT ⁸	SBRT Treatment ^{9,10}	Follow-Up ⁵ (Post-Radiation Treatment)					
				4-6 weeks	4 mos	6 ³ mos	9 mos	12 ³ mos	Yrs 2-5 Q 3-6 mos
Initial Consult	X								
Demographics	X								
History / Physical Exam	X			X	X	X	X	X	X
Informed consent	X								
Biopsy (confirmed adenocarcinoma)	X								
Labs: CBC, CMP, CA19-9		X ⁶		X	X	X	X	X	X
Post-op complication assessment (appendix 6)				X					
Negative Pregnancy Test ⁷		X							
Seed Placement (EUS, CT, intraoperatively)		X							
Simulation Scan		X							
Radiologic Evaluation (CT)		X		X ²	X	X	X	X	X
QoL Questionnaire		X		X	X ⁴	X	X ⁴	X	X
AE Evaluation	X			X	X	X	X	X	X
Research tubes		X		X ¹¹					

1 - CT pancreas or chest/abdomen/pelvis, as per treating physician, required pre- and post-SBRT.
 2 - If being reevaluated for resection, scans will be conducted at 4-6 weeks or as determined necessary by treating physician.
 3 - It is preferred that patients have the 6MFU and 12MFU evaluation and imaging at the treating institution. Other evaluations may be done at a local center however records must be submitted to SBRT treating facility.
 4 - QoL questionnaires may be completed and returned by mail if preferred.
 5 - Follow-up appointments have a +/- 30 day tolerance window. (ex. 6MFU may occur between 5-7 months)
 6 - Pre-SBRT labs should be done within 2 weeks prior to treatment.
 7 - Pregnancy test by urine or serum, for women who are not post-menopausal as defined in Appendix III.
 8 - Pre-SBRT procedures should be completed within 45 days of beginning treatment.
 9 - It is recommended that patients discontinue any chemotherapy one week prior to SBRT
 10 - Ideally all 5 fractions should be delivered Monday through Friday; however, treatment may be delivered over 2 weeks, as long as the patient receives at least 2 fractions per week.
 11- Pre-surgery

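### Patients without histologic confirmation can enter under Section V, and no rule in Section IX stops a tumor-free specimen in such a patient from counting as a pathologic complete response

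*Combined protocol and SAP*

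**What the plan says.** Four places in the combined protocol and SAP deal with histology at entry.

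- **Protocol Synopsis, Inclusion Criteria:** "Histologically confirmed pancreatic adenocarcinoma of the head and/or body; at least the majority of the histopathologic specimen must be identified as adenocarcinoma". No exception is given.
- **Section IV, Pre-Linac based SBRT Tests, Procedures, and Planning:** the items to be completed before SBRT include "Pathologic confirmation of malignancy". No exception is given. The note beside it makes core biopsies at fiducial placement optional, but not the confirmation itself.
- **Appendix I, Study Calendar:** the row that begins "Biopsy (confirmed adenocarcinoma" is marked at the pre-study visit and has no footnote.
- **Section V, Inclusion Criteria:** "Histologically confirmed adenocarcinoma of the pancreatic head and/or body; at least the majority of the histopathologic specimen must be identified as adenocarcinoma", followed by the exception "If histological confirmation of adenocarcinoma cannot be obtained by biopsy, the following procedures may be employed". The procedures are a repeat biopsy attempt and presentation at tumor board, where one of two findings suffices: "a rising CA 19-9 or radiographic evidence of pancreas tumor on MRI, CT, and/or PET scan then the patient can be considered for treatment on" (that is, on this study). If these cannot be met, the patient is not a candidate.

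The analysis side is in Section IX, Supplementary Analysis Plans: "The histopathologic response rate is defined as number of patients achieved CR or PR determined according to histopathologic examination", divided by the number of evaluable patients. Evaluable patients are those who meet eligibility, are confirmed by central review, have consented and have begun any dose of treatment. What central review covers is not stated. The only review described at enrolment, in the Study Overview of the same section, is radiologic.

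Pathologic complete response rate and margin positivity rate are secondary objectives in Section I. Section IX asks only for a point estimate and confidence interval for the response and margin rates.

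**The concern.** The same patient is eligible under Section V and fails the criterion as written in the Synopsis, Section IV and Appendix I. The secondary-endpoint denominator is built on meeting the eligibility criteria, so the conflict carries straight into the analysis.

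Pathologic complete response means that tumor known to be present before treatment is gone from the specimen. If adenocarcinoma was never shown, a specimen without carcinoma has two explanations: the treatment worked, or there was no carcinoma to begin with. The plan has no rule that separates them. At 20 patients, one misclassified specimen moves the rate visibly. The same patient would also enter the margin, recurrence and survival summaries and, if resected, the completion-of-therapy count.

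**Working it through.** **1. The plan's own figures.** Section IX gives no target, power or sample size for pathologic response, so there is nothing to reproduce there. The nearest design figures belong to the completion rule (at least 6 of 20). With X binomial(20, p):

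- P(X ≤ 5 | p = 0.20) = 0.804; the plan says more than 80%.
- P(X ≤ 5 | p = 0.40) = 0.126; the plan says less than 13%.

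Both reproduce.

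**2. Following one patient through the text.** Suppose two biopsies are non-diagnostic and imaging shows a pancreatic tumor.

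| Step | Place | Result |
|---|---|---|
| Entry | Section V | Can be considered after tumor board |
| Entry | Synopsis, Section IV, Appendix I | Requirement not met |
| Evaluable set | Section IX | In, if eligible under Section V and passed by central review (content not described) |
| Specimen shows no carcinoma | Section IX | No definition of histopathologic CR or PR; no rule for this case |
| CR definitions that do exist | Sections XII and XIII | Radiographic and symptom-based only |

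Nothing directs that this patient be scored as a complete response, and nothing forbids it.

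**3. Effect on the response rate.** Inputs: n = 20 (Section IX, Sample Size); r true responders and k patients without cancer scored as complete response, both assumed because the documents give neither. Reported rate = (r + k)/20; rate with those patients excluded = r/(20 − k); intervals are exact (Clopper-Pearson) 95%.

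| r | k | Reported | Excluded |
|---|---|---|---|
| 2 | 0 | 2/20 = 10.0% (1.2 to 31.7) | the same |
| 2 | 1 | 3/20 = 15.0% (3.2 to 37.9) | 2/19 = 10.5% (1.3 to 33.1) |
| 0 | 1 | 1/20 = 5.0% (0.1 to 24.9) | 0/19 = 0% (0 to 17.6) |

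One patient moved from non-responder to complete response adds 1/20 = 5 percentage points. Against exclusion, the r = 2 example differs by 15.0 − 10.5 = 4.5 points.

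**4. The other direction.** If the one never-confirmed patient is not resected, or has another malignancy in the specimen and is scored a non-responder, the rate with r = 2 is 2/20 = 10.0% instead of 2/19 = 10.5%. That patient dilutes the rate by 0.5 points.

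**5. Completion count, as illustration only.** Assume that k patients without cancer all complete therapy with R0 resection and that the others have a true 20% rate. The chance of reaching 6 of 20 is then P(X ≥ 6 − k), with X binomial(20 − k, 0.20): 0.196 for k = 0 and 0.327 for k = 1.

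**The case against.** The strongest reply is that the scenario needs a chain of events: an inconclusive repeat biopsy, tumor board acceptance, passage through central review, resection, a specimen without carcinoma, and a pathologist who calls that a complete response. Section V also requires the tumor board to judge the tumor at least borderline resectable, and it says only that the patient can be considered. The endpoint is descriptive, and the intervals in the example overlap almost entirely.

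Most of this stands as a limit on likelihood and weight. It does not remove the conflict between the four places or supply the missing rule.

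A reader might infer more than the text supports:

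- *That the plan would score this patient as a complete response.* Section IX does not define histopathologic complete response, and central review might exclude the patient. The documents support only that it could happen.
- *That the error always favors the treatment.* Step 4 shows dilution. Recurrence and survival could also move either way if the lesion is a different malignancy.
- *That the pathologic rates drive the phase II decision.* Section IX rests that decision on accrual, toxicity with treatment delay, and completion of therapy. The pathologic response and margin positivity rates trigger no rule. Only the completion count, which includes R0 or R1 resection, touches a decision.
- *That several unconfirmed patients would shift the rate by 5 points each.* That equates unconfirmed with cancer-free and requires every one to be resected and scored as a complete response.

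**Conclusion.** The concern holds in a limited form. The eligibility text contradicts itself on whether histology is required, and the histopathologic response rate rests on that eligibility with no histology condition of its own. Followed as written, the rate could include a patient who never had adenocarcinoma, counted as a complete response.

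The size is up to 5 percentage points per such patient at n = 20. The two-responder baseline and the single such patient in the example are assumptions; the documents give no rate of unconfirmed or benign cases, and the true number may be zero. The endpoint affected is secondary and descriptive. The correction is worth making because it is cheap and must be fixed before specimens are read.

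**What to change.** 1. Reconcile the Synopsis, Section IV, Section V and Appendix I on whether histologic confirmation is required and whether an exception exists.
2. In Section IX, define histopathologic CR and PR and state what central review covers.
3. Report pathologic response and complete response in patients with adenocarcinoma confirmed before SBRT. Do not let the resection specimen decide who enters this denominator: a never-confirmed patient with residual tumor would enter while a never-confirmed true complete responder would drop out, which selects on the outcome.
4. Do not score a never-confirmed patient with a tumor-free specimen as a complete response. List every patient entered through the exception separately, with the specimen result, and show the all-evaluable rate alongside. In the example this gives 2/19 = 10.5% with 2/20 = 10.0% beside it.
5. Apply the same restriction as a sensitivity analysis for margin status, recurrence, survival and the completion count. Keep all treated patients in the toxicity analysis.

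The cost is SAP wording and a slightly smaller denominator for a descriptive secondary endpoint. A genuine complete response in a never-confirmed patient would be left out of the main rate; the separate listing keeps it visible. No added patients or procedures are needed.
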